4.2. Selection of Study Population

The study population consists of adult patients of both sexes with a diagnosis of definite or probable dermatomyositis according to the Bohan and Peter criteria (1975); please refer to the protocol for a complete list of inclusion/exclusion criteria.

4.3. Randomization, Stratification and Blinding

All subjects qualified to participate in the study at Visit 2 (Baseline) will be block randomized to one of the 2 treatment arms: *octanorm* 0.5 g/kg/week or placebo (0.9% sodium chloride) in a balanced ratio of 1:1 by means of a permuted block randomization scheme; varying block sizes may be used to facilitate balanced enrolment.

The block size and the randomization scheme will only be available to the statisticians responsible for creating it, and the programmer implementing the scheme into the Interactive Response Technology (IRT) system. No information on treatment assignment will be communicated to study site personnel or to the sponsor or any CRO personnel responsible for the conduct of the study or the analysis of data, with the exception of medical emergencies as described in the protocol (section 5.6).

Each weekly infusion cycle will consist of 2 infusion sessions as described above. If a subject is randomized to placebo, the same volume with the same infusion rate will be applied as if the subject would have been randomized to *octanorm*.

In order to maintain the blind, IgG plasma level results performed at the central laboratory will not be revealed to the Sponsor, the Investigator and other blinded personnel at the study site.

Only after completion of all procedures related to data cleaning, the medical review of the data, the finalization of the statistical analysis plan, the agreement on the final subject disposition, and the formal database lock the blind will be broken and the individual treatment assignment will be added to the clinical database for analysis.

Property of Octapharma. Do not copy or distribute without written permission.

5. Sequence of Planned Analyses

5.1. Final Analyses and Reporting

As described above, all patients should be followed for 32 weeks of SCIG treatment or until a clinically important deterioration occurs. The blind will be maintained throughout the complete study, including patients withdrawn from the study for deterioration and treated with IGIV as a rescue treatment. Only in case of a medical emergency individual patients may be unblinded; otherwise the blind will not be broken before all subjects have completed the entire study and the final database has been locked and released for analysis according to the applicable standard operating procedures.

This process includes a data review, the identification and classification of any protocol deviations as detailed in section 7, and thus the subject disposition with respect to the analysis populations. All final, planned analyses identified in the protocol and in this SAP will be performed only after the last subject has completed the study, the subject disposition has been agreed and documented, and the final SAP has been approved.

Key statistics and study results will be made available to the study team following database lock and prior to completion of the final CSR by means of tables, figures and listings.

Any, post-hoc, exploratory analyses completed to support planned study analyses, which were not identified in the final SAP, will be documented and reported in the CSR or its appendices. Any results from such unplanned analyses will also be clearly identified in the text of the CSR.

Deviations from the analyses described in the protocol, this SAP or its appendices will be described and justified in a protocol amendment and/or in the final CSR.

No interim analysis is planned.

6. Sample Size Determination

The sample size calculation is based on the target parameter for the evaluation of the primary endpoint, i.e. the proportions of patients with clinically important deterioration in the active treatment arm (*octanorm* 0.5 g/kg/week) and the placebo arm until the end of the 32 week treatment period. Patients who drop out prematurely or receive rescue treatment for any reason will also be analyzed as patients with clinically important deterioration.

The following assumptions for the true proportion of patients to be analyzed as patients with clinically important deterioration, which will include all dropouts, were chosen for the sample size calculation after thorough discussion with Steering Committee members involved in the treatment of DM patients:

- *Octanorm* arm: 27% (this corresponds to a failure rate of 18.89% in patients randomized to *octanorm* who completed the study per protocol plus a 10% drop-out rate)
- Placebo arm: 58% (this corresponds to a failure rate of 53.33% in patients randomised to Placebo who completed the study per protocol plus a 10% drop-out rate)

The pair of hypotheses tested is: $H_0: P_O = P_P$ vs. $H_A: P_O \neq P_P$

where P_O and P_P denote the proportions of patients with clinically important deterioration in the *octanorm* and placebo arm respectively.

With these assumptions, a sample size of 39 patients per treatment arm will be needed to achieve a power of 80% to detect a difference between the group proportions, using the Pearson Chi-square Test for Proportion Difference at a significance level of $\alpha=0.05$. It is therefore planned to enroll a minimum of 78 patients, randomized to the two treatments groups in a balanced 1:1 ratio.

6.1. Subject Replacement Policy

Patients withdrawn from the study because of safety or efficacy reasons will not be replaced; these premature terminations will in any case establish clinically important deteriorations and be analyzed as such. Patients withdrawn from the study for any other reason, e.g. major protocol violation, pregnancy or administrative reasons will also not be replaced. However, if there is a substantial number of withdrawals, the Sponsor and the Coordinating Investigator will consult with the IDMC (without breaking the blind), and decide on a possible replacement policy.

6.2. Premature Termination of the Study

Both, the responsible Investigators and the Sponsor, reserve the right to terminate the study at any time. Should this be necessary, the procedures will be arranged on an individual study basis after review and consultation by both parties. In terminating the study, the Sponsor and the Investigator will ensure that adequate consideration is given to the protection of the subjects' interests. Premature termination will be notified in accordance with applicable regulatory requirements. Please refer to the protocol (section 6.2.3) for further details on premature termination, in particular for the exact stopping criteria triggering the early termination of the entire study for safety reasons (6.2.3.1).

In case the study is terminated prematurely, the SAP will be revised to address all issues arising from such special circumstances, and to confirm or redefine the scope of the analysis.

7. Analysis Populations

The following populations will be considered for the statistical analysis:

The all patients enrolled set includes all patients with a non-empty case report form who signed the informed consent.

The safety analysis set (SAF) consists of all subjects who received at least part of one infusion of *octanorm* or placebo.

The full analysis set (FAS) is defined according to the intention-to-treat (ITT) principle and consists of all randomized subjects of the SAF who satisfy all major eligibility criteria and for whom any post screening data are available. It is expected that the FAS will coincide with the safety set, only patients who could otherwise only be regarded as artefacts in the final ITT analysis would be excluded from the FAS. Examples for such special circumstances would include a wrong diagnosis (if it turns out that a patient does in fact not suffer from dermatomyositis) or if the patient was in fact not previously treated with IgG. Also the exclusion of patients without any data post randomization will help to avoid artefacts that cannot contribute any meaningful data to the analysis; this cannot introduce any bias due to the blinded design of the study.

The per-protocol set (PP) consists of all subjects of the FAS excluding those with significant protocol deviations that may have an impact on the analysis of the primary endpoint. This is the set of subjects for whom the primary endpoint can be evaluated as planned.

Only significant protocol deviations with the potential to affect the study results significantly, or to invalidate the interpretation of the data obtained, will lead to exclusion of subjects from the PP set; protocol deviations to be considered will include (but will not be limited to):

- Violations of the study entry criteria
- Withdrawal criteria that developed during the study
- Wrong treatment or incorrect dose
- Prohibited concomitant medication
- Subjects who had no CSM or CDASI at Week 32

Protocol deviations during the safety follow up are irrelevant for the definition of the PP set.

Analysis of the safety endpoints will be based on the safety set.

The primary endpoint will be evaluated on basis of the FAS and the PP set. The intent-to-treat analysis of the FAS population is considered the primary study outcome, and will be presented first in the statistical output. The PP analysis will be conducted to assess the robustness of the result. The level of accordance between these two analyses will be discussed in the study report; in case the p-values obtained differ in terms of significance (i.e. above/below 0.05), this will be especially stressed.

All other analyses will be based on the FAS set and/or the PP set as appropriate; this will be specified in detail in the list of all tables, figures and listings.

Repetition of an analysis in the PP set might be skipped in case the PP population differs from the FAS by no more than 5 subjects; this does however not apply for the primary endpoint evaluation.

The membership of each subject in the respective analysis populations will be determined before the statistical analysis in a data review meeting by a panel consisting of a medical expert from the sponsor, the clinical project manager, the data manager and the study statistician.

All protocol deviations documented during the conduct of the study or identified at the data review process prior to DB lock will be reviewed and classified as minor or major and with respect to their significance for the planned analyses. Only significant protocol deviations with the potential to affect the study results or to invalidate the interpretation of the data obtained will lead to exclusion of

subjects from the PP sets. This classification of protocol deviations is the joint responsibility of the clinical study manager, the study statistician, and Octapharma's responsible medical expert, and will be agreed and documented before the database is locked and the statistical analyses are performed.

Property of Octapharma. Do not copy or distribute without written permission.

8. General Issues for Statistical Analysis

The primary, confirmatory analysis will be the comparison between *octanorm* and placebo with respect to the proportion of patients with clinically important deterioration until week 32.

In addition to the confirmatory evaluation of the primary endpoint, all data collected will be listed and presented by means of descriptive statistics and comparisons between the treatment groups.

In general, statistical summaries will be presented for all patients overall and by treatment group in a side-by-side manner.

Descriptive subgroup analyses will be performed with respect to age, sex, race (if the study population is sufficiently diverse for meaningful comparisons), and region (U.S. vs. Non-U.S.); in particular the primary efficacy outcome will be presented for each of these subgroups.

Continuous, quantitative variable summaries will in general include the number of subjects with non-missing values (N), mean, standard deviation, median, minimum and maximum, 1st and 3rd quartile.

If appropriate, continuous variables may be categorized and additionally treated as ordinal variables.

Categorical, qualitative variable summaries will include the frequency and percentage of subjects who are in the particular category. In general the denominator for the percentage calculation will be based upon the total number of subjects in the analysis population unless otherwise specified.

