### 4.3 Withdrawal and Replacement of Subjects/Patients

#### 4.3.1 Premature Subject/Patient Withdrawal

Subjects have the right to withdraw from the study at any time for any reason, without the need to justify their decision. The Investigator also has the right to withdraw subjects in case of AEs, poor compliance, or other reasons. Since an excessive rate of withdrawals can render the study non-interpretable, any unnecessary withdrawal by investigator's decision should be avoided.

For any withdrawals after study entry, the Investigator will obtain all the required details and document the reason(s) for discontinuation. If the reason for withdrawal of a subject/patient is an AE, the main specific event or laboratory test will be recorded, and the Investigator will make thorough efforts to clearly document the outcome.

Should a subject decide to withdraw, the Investigator will make the best efforts to complete and report the observations. The Investigator will document the reason(s) for withdrawal of each subject in the eCRF.

Subjects who terminate the study prematurely are drop-outs. The Investigator has to organize the Drop-out visit which is identical to the Termination visit procedures.

Other reasons for premature termination of subjects may be:

1. Withdrawal of subject's consent.
2. Deterioration of DM.
3. Pregnant subjects will be immediately excluded from the study.
4. Investigator's opinion that the subject may be severely harmed if he/she continues trial participation, namely by the treatment and procedures according to the study protocol.
5. Occurrence of a disease which interferes with the study treatment or represents an exclusion criterion.
6. Administration of IgG other than *octanorm*.

"Clinically important deterioration" is defined as follows:

- 1) MMT-8 worsening  $\geq 6$  points (scale of 150) OR CDASI (Total Activity Score) worsening  $\geq 5$  points,  
AND
- 2) Physician's Global Disease Activity VAS worsening  $\geq 2$  cm.

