In case of clinically important deterioration during the treatment period, subjects will be discontinued from the study, will undergo a termination visit and may optionally receive Octagam 10% as IGIV rescue medication (2g/kg BW one time, provided by the sponsor) or rescue treatment according to standard of care at the site by the treating physician. Octagam 10% or any other commercially available IGIV as optional IGIV rescue medication can be also reimbursed by the sponsor (2g/kg BW one time). IGIV as rescue medication should be administered with infusion rate not higher than 0.04 mL/kg/min (240 mg/kg/h).

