#### **4.5 Relevant Protocol Deviations**

Deviations from the protocol should be avoided. A complete list of all minor and major deviations will be compiled and provided for preparation of the clinical study report.

Examples of relevant protocol deviations that will be addressed are:

- Subjects who entered the study even though they did not satisfy the entry criteria.
- Subjects who developed withdrawal criteria during the study (see Section 4.3.1).
- Subjects who received the wrong treatment or incorrect dose (also see Section 5.4).
- Subjects who received an excluded concomitant treatment or a change in the permitted DM-related therapies.
- Subjects who had no CSM or CDASI at Week 32 or Drop-Out Visit.

In case of any major protocol deviation, the Investigator and Octapharma will decide on the further participation of the subject/patient in this study after having discussed all relevant aspects.

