**6.1.10 Termination Visit (Week 32 or Drop-out Visit)**

The Termination Visit is performed at Week 32.

The following assessments will be performed:

- SF-36v2.
- Patient diary check.

- Physical examination.
- Vital signs and body weight.
- Blood sample for safety laboratory (hematology and clinical chemistry).
- Blood sample for additional safety lab parameters (serum haptoglobin, plasma-free hemoglobin).
- Direct Coombs' test (if positive, the antibodies responsible for the positive Coombs' test will be eluted to investigate their specificity (anti-A, anti-B or anti-D)).
- Urinalysis.
- Blood sample for serum IgG.
- Blood samples for enzymes.
- Blood sample for viral markers.
- Blood sample for biomarkers of disease activity.
- CSM.
- CDASI.
- Wells probability score for DVT. If score is likely for DVT ( $\geq 2$  points), perform Doppler scan and take blood sample for D-dimers.
- Wells probability score for PE.
- Monitoring of AEs.
- Assessment of local injection site reactions.
- Documentation of concomitant therapy.
- Pregnancy test (in WOCBP).
- Visit registration in IRT.

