#### **9.5 Populations for Analysis**

The following populations will be considered for the statistical analysis:

The all patients enrolled set includes all patients with a non-empty case report form who signed the informed consent.

The safety analysis set (SAF) consists of all subjects who received at least part of one infusion of *octanorm* or placebo.

The full analysis set (FAS) is defined according to the intention-to-treat principle and consists of all randomized subjects of the SAF who satisfy all major eligibility criteria and for whom any post screening data are available. It is expected that the FAS will coincide with the safety set, only patients who could otherwise only be regarded as artefacts in the final ITT analysis would be excluded from the FAS. Examples for such special circumstances would include a wrong diagnosis (if it turns out that a patient does in fact not suffer from dermatomyositis) or if the patient was in fact not previously treated with IgG. Also the exclusion of patients without any data post randomization will help to avoid artefacts that cannot contribute any meaningful data to the analysis; this cannot introduce any bias due to the blinded design of the study.

The per-protocol set (PP) consists of all subjects of the FAS excluding those with significant protocol deviations that may have an impact on the analysis of the primary endpoint. This is the set of subjects for whom the primary endpoint can be evaluated as planned.

Only significant protocol deviations with the potential to affect the study results significantly, or to invalidate the interpretation of the data obtained, will lead to exclusion of subjects from the PP set; protocol deviations to be considered will include (but will not be limited to):

- Violations of the study entry criteria
- Withdrawal criteria that developed during the study
- Wrong treatment or incorrect dose
- Prohibited concomitant therapy
- Subjects who had no CSM or CDASI at Week 32.

Protocol deviations during the safety follow up are irrelevant for the definition of this population.

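### Read literally, the per-protocol exclusion list removes patients because they had the primary event before Week 32; it conflicts with Protocol 4.5 and SAP 4.1, and nothing says deterioration is not an exclusion

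*SAP*

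**What the plan says.** SAP Section 7 and Protocol 9.5 define PP as the FAS minus patients with significant deviations, and give the same list of deviations to be considered. Two items matter here:

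- "Withdrawal criteria that developed during the study"
- "Subjects who had no CSM or CDASI at Week 32"

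Protocol 4.5 has a parallel list. Its withdrawal item refers the reader to Section 4.3.1, where "Deterioration of DM" is one of the reasons for premature termination. Its assessment item is wider than the one in SAP 7: "Subjects who had no CSM or CDASI at Week 32 or Drop-Out Visit".

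Protocol 4.3.1 also says what follows the primary event: "In case of clinically important deterioration during the treatment period, subjects will be discontinued from the study, will undergo a termination visit". SAP 4.1 calls that visit a drop-out visit and treats these patients as completers, because they reached the primary endpoint. SAP 7 describes PP as the patients in whom the primary endpoint can be evaluated as planned.

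**The concern.** A patient who meets the deterioration definition at, say, Week 16 leaves the study then and has no Week 32 CSM or CDASI. As worded, that patient meets both PP items. The patient has not departed from the protocol; the patient has had the outcome that the trial counts. Applied literally, the list conditions PP membership on the primary outcome and removes more patients from the arm with more events.

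PP is the stated robustness check on the primary result. SAP 7 and Protocol 9.7.1 promise to stress any FAS/PP disagreement on significance, and Protocol 9.7.2 makes essential differences the trigger for PP analyses of the secondary endpoints. PP could then look discordant because it had lost its events, not because the FAS result is fragile.

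**Working it through.** **Text, side by side**

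| Place | What it implies for a patient with the event before Week 32 |
|---|---|
| SAP 7 and Protocol 9.5, Week 32 item | Meets it (no Week 32 assessment) |
| SAP 7 and Protocol 9.5, withdrawal item, read with Protocol 4.5 and 4.3.1 | Meets it |
| Protocol 4.5, assessment item | Does not meet it if assessed at the Drop-Out Visit |
| SAP 4.1 | Completer |
| SAP 7, purpose of PP | Evaluable as planned |

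The Protocol therefore disagrees with itself (4.5 against 9.5), and the SAP carries the narrower wording.

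**Inputs** (Protocol 9.1, 9.2; SAP 6): 39 per arm; two-sided Pearson chi-square at 0.05; failure 53.33% (placebo) and 18.89% (octanorm) among those completing per protocol; 10% other drop-outs counted as failures.

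**The plan's own figures**

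- Mixture: 0.9 × 53.33% + 10% = 58.0%; 0.9 × 18.89% + 10% = 27.0%.
- n per arm = [1.960 × √(2 × 0.425 × 0.575) + 0.842 × √(0.58 × 0.42 + 0.27 × 0.73)]² / 0.31² = 38.7, so 39. This reproduces the plan. Power at 39 per arm is 80.3% by the normal formula and 80.9% exactly.

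**Expected PP set with deteriorators kept and other drop-outs outside PP**

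- Patients: 0.9 × 39 = 35.1 per arm.
- Events: 35.1 × 0.5333 = 18.7 on placebo and 35.1 × 0.1889 = 6.6 on octanorm, about 25.3 in all.
- Power: 87%.

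**Literal PP set.** Let f be the share of deteriorations first met at Week 32. The documents do not give f, so it is varied. An arm with D expected deteriorations keeps f × D events among 35.1 − (1 − f) × D patients. For placebo at f = 12.5%: 2.3 / 18.7 = 12.5%. For octanorm: 0.8 / 29.3 = 2.8%.

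There are eight scheduled post-baseline CSM/CDASI visits (Weeks 4 to 32). Even timing gives f = 1/8 = 12.5%. A constant per-visit hazard is 1 − (1 − 0.5333)^(1/8) = 0.0909 on placebo and 1 − (1 − 0.1889)^(1/8) = 0.0258 on octanorm, which gives f = 8.7% and 11.4%.

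Power comes from 400,000 simulated trials. In each arm, other drop-outs are Binomial(39, 0.10), and deteriorations are binomial among the rest. The test is the uncorrected chi-square, p < 0.05 favouring octanorm. FAS power is 81.0%.

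| f | Expected PP rates, placebo vs octanorm | Deteriorations lost, of 25.3 | Literal PP power | FAS significant, PP not |
|---|---|---|---|---|
| Constant hazard | 9.1% vs 2.6% | 23.0 | 15% | 67% |
| 12.5% | 12.5% vs 2.8% | 22.2 | 25% | 57% |
| 25% | 22.2% vs 5.5% | 19.0 | 45% | 39% |
| 50% | 36.4% vs 10.4% | 12.7 | 68% | 18% |
| 75% | 46.2% vs 14.9% | 6.3 | 80% | 7% |

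An exact calculation at fixed, rounded arm sizes gives similar power: 22%, 44%, 71% and 78% for f = 12.5%, 25%, 50% and 75%.

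**Partial application.** If the panel removes only 25%, 50% or 75% of early deteriorators (constant hazard), PP power is 81%, 69% or 50%.

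**Deteriorators kept.** PP power is 87%, 84% or 81% if none, half or all of the other drop-outs are in PP. The chance that FAS is significant and PP is not is then 0% to 2%.

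**The case against.** The strongest reply is that the plan plainly means to keep these patients.

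- The list is of deviations to be considered. Only significant ones exclude, and a panel decides before the analysis. A patient discontinued as the protocol requires has not deviated. This stands: exclusion is not automatic. But the panel has a list that these patients meet twice and no rule protecting them.
- Week 32 may be shorthand for the termination slot. Protocol 4.3.1 says "The Investigator has to organize the Drop-out visit which is identical to the Termination visit procedures", the heading of Protocol 6.1.10 and the Table 1 column join the two visits, and SAP 8.4 lets the termination visit fall earlier. This is a fair reading. The text of 6.1.10 does say "The Termination Visit is performed at Week 32", but its own heading weakens that as evidence for the literal reading. Protocol 4.5 still names the two visits separately, and the shorthand does not touch the withdrawal item, which Protocol 4.5 shares.
- The expert-adjudicated analysis of withdrawals is planned in PP as well as FAS (Protocol 9.7.1, SAP 10.1), and the sample-size text counts failures among those completing per protocol. Both suggest that deteriorators belong in PP. They also conflict with the list as worded, so they support the same correction.
- The low power figures depend on unknown event timing and on a panel discarding most of the observed events. That is correct, and is why a range is shown. Seven of the eight visits precede Week 32, but that does not fix the timing. Most events are lost only if fewer than half are first met at Week 32.

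**Conclusion.** The concern holds. The PP list, as worded, captures patients for having had the primary event early, contradicts Protocol 4.5 (on the Week 32 item) and SAP 4.1, and no sentence overrides it. Intent to keep these patients can be inferred but is not stated.

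The size is conditional on the panel applying the list literally, on the planning rates, and on timing. For f from about 9–11% (constant hazard) to 75%, PP power runs from 15% to 80% instead of 87%, and FAS/PP discordance from 67% to 7% instead of about 2% (other drop-outs outside PP throughout). The harm is confined to the PP robustness analysis and what it triggers. The FAS primary test, alpha and sample size are intact, and no false efficacy claim arises. It should be fixed.

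**What to change.** In SAP Section 7, before database lock and unblinding:

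1. Replace the Week 32 bullet with the Protocol 4.5 wording: "Subjects who had no CSM or CDASI at Week 32 or Drop-Out Visit".
2. Add one sentence: *Clinically important deterioration, and the discontinuation it leads to, do not in themselves exclude a patient from the PP set; such a patient counts as an event unless a separate significant deviation applies.* This is needed because change 1 leaves the withdrawal item untouched.

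Align Protocol 9.5 at the next amendment, or describe the change in the study report, as Protocol 9.11 allows.

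The cost is one bullet and one sentence, with no new data; aligning Protocol 9.5 needs an amendment. One side effect of change 1 is that other drop-outs assessed at the Drop-Out Visit are no longer removed by that bullet and count as PP failures unless another deviation applies. That is the 81% to 87% power range above. Settling the wording after unblinding would look driven by the result.
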